Appendix 2: NSAA Score Sheet

| Activity | 2 | 1 | 0 |
|------------------------------------|--|--|--|
| 1. Stand | Stands upright, still and symmetrically, without compensation (with heels flat and legs in neutral) for minimum count of 3 seconds | Stands still but with some degree of compensation (e.g. on toes or with legs abducted or with bottom stuck out) for minimum count of 3 seconds | Cannot stand still or independently, needs support (even minimal) |
| 2. Walk | Walks with heel-toe or flat-footed gait pattern | Persistent or habitual toe walker, unable to heel-toe consistently | Loss of independent ambulation – may use KAFOs or walk short distances with assistance |
| 3. Stand up from chair | Keeping arms folded Starting position 90° hips and knees, feet on floor/supported on a box step. | With help from thighs or push on chair or prone turn | Unable |
| 4. Stand on one leg - right | Able to stand in a relaxed manner (no fixation) for count of 3 seconds | Stands but either momentarily or needs a lot of fixation e.g. by knees tightly adducted or other trick | Unable |
| 5. Stand on one leg - left | Able to stand in a relaxed manner (no fixation) for count of 3 seconds | Stands but either momentarily or needs a lot of fixation e.g. by knees tightly adducted or other trick | Unable |
| 6. Climb box step - right | Faces step – no support needed | Goes up sideways or needs support | Unable |
| 7. Climb box step - left | Faces step – no support needed | Goes up sideways or needs support | Unable |
| 8. Descend box step - right | Faces forward, climbs down controlling weight bearing leg. No support needed | Sideways, skips down or needs support | Unable |
| 9. Descend box step - left | Faces forward, climbs down controlling weight bearing leg. No support needed | Sideways, skips down or needs support | Unable |
| 10. Gets to sitting | Starts in supine – may use one hand to assist | Self assistance e.g. – pulls on legs or uses head-on-hands or head flexed to floor | Unable |
| 11. Rise from floor | From supine – no evidence of Gowers' manoeuvre* | Gowers' evident | (a) NEEDS to use external support object e.g. chair OR (b) Unable |
| 12. Lifts head | In supine, head must be lifted in mid-line. Chin moves towards chest | Head is lifted but through side flexion or with no neck flexion | Unable |
| 13. Stands on heels | Both feet at the same time, clearly standing on heels only (acceptable to move a few steps to keep balance) for count of 3 | Flexes hip and only raises forefoot | Unable |
| 14. Jump | Both feet at the same time, clear the ground simultaneously | One foot after the other (skip) | Unable |
| 15. Hop right leg | Clears forefoot and heel off floor | Able bend knee and raise heel, no floor clearance | Unable |
| 16. Hop left leg | Clears forefoot and heel off floor | Able bend knee and raise heel, no floor clearance | Unable |
| 17. Run (10m) | Both feet off the ground (no double stance phase during running) | 'Duchenne jog' | Walk |

Appendix 3 The Scoring Algorithms for the Paediatric Outcomes Data Collection Instrument

The algorithm for the upper extremity and physical function core scale is as follows:

| Component | Value | Result |
|----------------------------|--|---|
| Notes: | | |
| | 
 Any item rated "5" (Too young for this activity) is considered missing and is not added into the scale. A minimum of 4 items must have valid answers to score this scale (including those marked "too young" as missing). | |
| Raw Score: | Sum of items Q1, Q2, Q3, Q4, Q5, Q6, Q8, Q32 | Value ranging: 8 to 32 (if all 8 questions are answered) |
| Mean of Items: | (sum of items Q1, Q2, Q3, Q4, Q5, Q6, Q8, Q32) / (number of non-missing items) | Value ranging: 1 to 4 |
| Standardized Score: | [(4 - mean of items) / 3] * 100 | Value ranging: 0 to 100 |

The algorithm for the transfer and basic mobility core scale is as follows:

| Component | Value | Result |
|----------------------------|--|---|
| Note: | | |
| | 
 Any item rated "5" (Too young for this activity) is considered missing and is not added into the scale. A minimum of 7 items must have valid answers to score this scale (including those marked "too young" as missing). | |
| | Q34 is RESCALED as follows: Q34rescaled = [(Q34 - 1)* 3/4] + 1 | Value ranging: 1 to 4 |
| | Q35 is RESCALED as follows: Q35rescaled = [(Q35 - 1)* 3/4] + 1 | Value ranging: 1 to 4 |
| Raw Score: | Sum of items Q7, Q21, Q24, Q25, Q28, Q29, Q30, Q31, Q33, Q34Rescaled, Q35Rescaled | Value ranging: 11 to 44 (if all 11 questions are answered) |
| Mean of Items: | (sum of items Q7, Q21, Q24, Q25, Q28, Q29, Q30, Q31, Q33, Q34Rescaled, Q35Rescaled) / (number of non-missing items) | Value ranging: 1 to 4 |
| Standardized Score: | [(4 - mean of items) / 3] * 100 | Value ranging: 0 to 100 |

The algorithm for the sports and physical functioning core scale is as follows:

| Component | Value | Result |
|----------------------------|--|---|
| Note: | | |
| | 
 Any item rated "5" (Too young for this activity) is considered missing and is not added into the scale. A minimum of 6 items must have valid answers to score this scale (including those marked "too young" as missing). | |
| | Q26 is RESCALED as follows: $Q26_{\text{rescaled}} = [(Q26 - 1) * 3/4] + 1$ | Value ranging: 1 to 4 |
| | Q27 is RESCALED as follows: $Q27_{\text{rescaled}} = [(Q27 - 1) * 3/4] + 1$ | Value ranging: 1 to 4 |
| | Q36 is RECODED to MISSING if (Q36 = 4 and EITHER [Q42 = 1] or [Q43 = 1]) | Value ranging: 1 to 4 |
| | Q44 is RECODED to MISSING if (Q44 = 4 and EITHER [Q50 = 1] or [Q51 = 1]) | Value ranging: 1 to 4 |
| | Q52 is RECODED to MISSING if (Q52 = 4 and EITHER [Q58 = 1] or [Q59 = 1]) | Value ranging: 1 to 4 |
| | Q60 is RECODED and RESCALED as follows: Step #1: Q60 is RECODED to MISSING if (Q60 = 3 and Q65 = 1) | |
| | Step #2: If Q60 is not missing, $Q60_{\text{rescaled}} = [(Q60 - 1) * 3/2] + 1$ | Value ranging: 1 to 4 |
| | Q66 is RECODED and RESCALED as follows: Step #1: Q66 is RECODED to MISSING if (Q66 = 4) | |
| | Step #2: Q66 is RECODED to MISSING if (Q66 = 3 and EITHER [Q72 = 1] or [Q73 = 1]) | |
| | Step #3: If Q66 is not missing, $Q66_{\text{rescaled}} = [(Q66 - 1) * 3/2] + 1$ | Value ranging: 1 to 4 |
| Raw Score: | Sum of items Q18, Q19, Q20, Q22, Q23, Q26rescaled, Q27rescaled, Q36, Q44, Q52, Q60rescaled, Q66rescaled | Value ranging: 12 to 48 (if all 12 questions are answered) |
| Mean of Items: | $(\text{sum of items Q18, Q19, Q20, Q22, Q23, Q26rescaled, Q27rescaled, Q36, Q44, Q52, Q60rescaled, Q66rescaled}) / (\text{number of non-missing items})$ | Value ranging: 1 to 4 |
| Standardized Score: | $[(4 - \text{mean of items}) / 3] * 100$ | Value ranging: 0 to 100 |
| | | |

| The algorithm for the pain/comfort core scale is as follows: | | |
|--|---|---|
| Component | Value | Result |
| Notes: A minimum of 2 items must have valid answers to score this scale. | | |
| | Q17 is RESCALED as follows: $Q17_{\text{rescaled}} = [(4 - Q17) * 4/3] + 1$ | Value ranging: 1 to 5 |
| | Q75 is RESCALED as follows: $Q75_{\text{rescaled}} = [(Q75 - 1) * 4/5] + 1$ | Value ranging: 1 to 5 |
| Raw Score: | Sum of items Q17rescaled, Q75rescaled, Q76 | Value ranging: 3 to 15 (if all 3 questions are answered) |
| Mean of Items: | (sum of items Q17rescaled, Q75rescaled, Q76) / (number of non-missing items) | Value ranging: 1 to 5 |
| Standardized Score: | [(4 - {mean of items - 1}) / 4] * 100 | Value ranging: 0 to 100 |
| The algorithm for the happiness core scale is as follows: | | |
| Component | Value | Result |
| Notes: | | |
| 
 Any item rated "5" (Too young for this activity) is considered missing and is not added into the scale. A minimum of 3 items must have valid answers to score this scale (including those marked "too young" as missing). | | |
| Raw Score: | Sum of items Q10, Q11, Q12, Q13, Q14 | Value ranging: 5 to 25 (if all 5 questions are answered) |
| Mean of Items: | (sum of items Q10, Q11, Q12, Q13, Q14) / (number of non-missing items) | Value ranging: 1 to 5 |
| Standardized Score: | [(5 - mean of items) / 4] * 100 | Value ranging: 0 to 100 |
| The algorithm for the Global Function scale is as follows: | | |
| Component | Value | Result |
| Notes: | | |
| 
 If ANY of the four relevant scales are missing, this is not calculated. | | |
| Mean of Items: | (sum of "Standardized Score" values for scales: 'Upper extremity and physical function' + 'Transfer and basic mobility' + Sports and physical function' and 'Pain/comfort') /4 | Value ranging: 0 to 100 |

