5.2.5 Paediatric Outcomes Data Collection Instrument (PODCI)

The PODCI will be completed by the parent/carer. It consists of 86 questions from which five scales and one global scale are calculated (see [Appendix 3](#)). The five scales are:

- 1) Upper extremity and physical function core scales;
- 2) Transfer and basic mobility core scale,
- 3) Sports and physical functioning core scale,
- 4) Pain/comfort core scale and
- 5) Happiness core scale.

For each scale the mean score (referred to as the “mean of items”) will be calculated. If a question contained within a scale is not answered, that question is not included in the calculation of the mean score. For each scale there is a minimum number of questions that have to be answered, otherwise the score is considered missing.

The scale’s mean score is standardized into a score ranging between 0-100, where a higher score indicates fewer limitations due to DMD. The Standardized Score will be used in analyses.

The global functioning scale is calculated by taking the mean of the “standardized scores” from the following scales:

- 1) Upper extremity and physical function,
- 2) Transfer and basic mobility,
- 3) Sports and physical functioning and
- 4) Pain/comfort.

The scoring algorithms can be found in [Appendix 4](#).

No imputation will be used for missing PODCI scores.

Changes from baseline will be calculated for each scale standardized score and the global functioning scale score.

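### SAP Appendix 3 sets PODCI code 5 to missing on the Happiness scale, although that scale's own ranges and formula need 5 as the worst valid answer

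*SAP*

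**What the plan says.** SAP 5.2.5 uses the standardized PODCI scores in the analyses and says that "a higher score indicates fewer limitations due to DMD". Appendix 3 gives the scoring scale by scale.

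- **Happiness (Q10 to Q14, none rescaled).** The note reads "Any item rated '5' (Too young for this activity) is considered missing and is not added into the scale", and at least 3 valid items are required. The raw score is given as "Value ranging: 5 to 25 (if all 5 questions are answered"), the mean as 1 to 5, and the standardized score as (5 - mean)/4 x 100, from 0 to 100.
- **Upper extremity (8 items).** It carries the same note. The raw score is "Value ranging: 8 to 32 (if all 8 questions are answered"), so items run 1 to 4 and 5 lies outside the scale.
- **Pain/comfort (3 items).** This is the only other scale with a mean of 1 to 5. It has no rule on code 5, only "Notes: A minimum of 2 items must have valid answers to score this scale". Its raw score is "Value ranging: 3 to 15 (if all 3 questions are answered").
- **Transfer and Sports.** The note heads both. On Transfer, "Q34 is RESCALED as follows: Q34rescaled = [(Q34 - 1)* 3/4] + 1", with a stated result of 1 to 4, and Q35 is treated alike. On Sports, the line beginning "Q26 is RESCALED as follows" applies the same formula to Q26, and Q27 follows.

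The SAP gives no response labels. Protocol 6.5.4 places the questionnaire and scoring system in the Study Reference Manual.

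**The concern.** On Happiness the two instructions cannot both operate. A raw score of 25 from five unrescaled items requires a scored 5 on all five, and a standardized score of 0 requires a mean of 5. The note removes every 5. Confining the note to items on which 5 means too young does not help, because no Happiness item could then be one of them.

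On Q34, Q35, Q26 and Q27 the text is ambiguous rather than contradictory. The rescaling reaches its stated maximum only from a raw 5, yet the note above it exempts no item.

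If 5 is a real answer, the rule discards the worst answers and averages the rest. A boy who worsens from 4 to 5 usually gains points, and one who improves from 5 to 4 usually loses them. Happiness feeds the by-visit change tables (SAP 9.6.6) and the baseline summary and correlations (SAP 9.5). Transfer and Sports also feed the global function score, which enters the relationship plots of SAP 9.10.1 to 9.10.4.

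**Working it through.** All formulas and ranges come from SAP Appendix 3. Each scale is scored twice, with 5 as a valid answer and with 5 set to missing.

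**1. The stated Happiness ranges, 5 valid.** Raw: 5 x 1 = 5 to 5 x 5 = 25. Mean: 1 to 5. Score: (5 - 1)/4 x 100 = 100 down to (5 - 5)/4 x 100 = 0. Every stated range is reproduced.

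**2. Happiness with the note applied.** The largest item value is 4. Raw maximum: 5 x 4 = 20 (stated 25). Mean maximum: 4 (stated 5). Lowest score: (5 - 4)/4 x 100 = 25 (stated 0). With three or more 5s, fewer than 3 valid items remain and there is no score. Five 5s should score 0 but score nothing.

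**3. Size of the error on Happiness.** Let m be the mean of the items not rated 5. The excess is the score as written minus the score with 5 valid.

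- One 5: 25(5 - m) - 25(4 - 0.8m) = 25(1 - 0.2m), which is 20 at m = 1 and 5 at m = 4.
- Two 5s: 25(5 - m) - 25(3 - 0.6m) = 25(2 - 0.4m), which is 40 at m = 1 and 10 at m = 4.

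**4. Sign of a change on Happiness.**

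- One item moving from 4 to 5, the other four averaging m: as written the change is 25[(4m + 4)/5 - m] = 5(4 - m), between 0 and +15. With 5 valid it is -25/5 = -5.
- Example: 3,3,3,4,4 has mean 3.4 and score 40. After worsening to 3,3,3,5,5, the note leaves mean 3 and score 50. With 5 valid the mean is 3.8 and the score 30.

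**5. Rescaled items.** (5 - 1) x 3/4 + 1 = 4, the stated maximum; (4 - 1) x 3/4 + 1 = 3.25. The stated raw maxima, 44 for Transfer and 48 for Sports, also need 5: without it they are 36 + 2 x 3.25 = 42.5 and 40 + 2 x 3.25 = 46.5.

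**6. Transfer and Sports, if the note is applied to raw codes.** Let m be the mean of the other items (9 on Transfer, 10 on Sports), with both rescaled items at raw 5.

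- Transfer excess: (100/3)[(9m + 8)/11 - m] = (200/33)(4 - m)
- Sports excess: (100/3)[(10m + 8)/12 - m] = (50/9)(4 - m)

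The global score averages four scales, so it moves by a quarter of each.

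| Other items at | Transfer excess | Global, via Transfer | Sports excess | Global, via Sports |
|---|---|---|---|---|
| 4 | 0 | 0 | 0 | 0 |
| 3 | 6.1 | 1.5 | 5.6 | 1.4 |
| 2 | 12.1 | 3.0 | 11.1 | 2.8 |
| 1 | 18.2 | 4.5 | 16.7 | 4.2 |

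With only one of Q34 and Q35 at 5 and the other at 4, the Transfer excess is 3.0 to 8.4 for the other items at 3 down to 1 (0.8 to 2.1 on the global score).

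**7. Sign of a change on Transfer.** With the other items at 2 and both Q34 and Q35 moving from 4 to 5, the starting score is (4 - 24.5/11)/3 x 100 = 59.1. As written it goes to 66.7 (+7.6); with 5 valid, to 54.5 (-4.5). Moving back from 5 to 4 gives -7.6 instead of +4.5. The change as written is (100/3)(6.5 - 2m)/11, so the sign reverses only if m is below 3.25. The same threshold holds on Sports.

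**8. Group mean, as an assumed range.** Take 40 boys (Cohorts 1 and 2), with one net boy moving to 5 on both Q34 and Q35. Mean Transfer change shifts by 6.1/40 = 0.15 to 18.2/40 = 0.45 with his other items at 3 down to 1, and by 0 with them at 4. Mean global change shifts by 0.04 to 0.11, or 0.

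**The case against.** The strongest reply concerns reach. The firm contradiction sits in Happiness, which is outside the global score and appears only in descriptive and baseline tables. Everything that reaches the global score depends on Q34, Q35, Q26 and Q27, and there the text leans towards the harmless reading. The note identifies 5 by its too-young label, the 3/4 factor makes sense only for codes 1 to 5, and the Sports box states its other missing codes item by item (Q66 = 4, for example) but none for Q26 or Q27.

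Much of this stands. Those four items are a matter for clarification, and their figures apply only if the note is applied to raw codes. Three further points are also fair. The Transfer and Sports excess falls to zero when the other items are all at 4. Nothing in the documents says in which direction parent-rated Happiness moves over 48 weeks. And a code other than 5 might carry the too-young meaning on some items.

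None of this reconciles the Happiness box with itself. A programmer following Appendix 3 has to choose between the note and the ranges, and the choice decides how the worst answers are scored.

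**Conclusion.** The concern holds. The Happiness rule is wrong as written: its note and its ranges exclude each other, and applying the note inflates the score by 5 to 40 points when one or two items are rated 5 and removes the score when three or more are. The appendix suggests that the note is the misplaced part, since it fits Upper extremity and is absent from Pain/comfort, but only the code list can settle that.

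For Q34, Q35, Q26 and Q27 the plan is ambiguous. If the note is applied to their raw codes, the global function score is up to 4.5 points too high through Transfer and up to 4.2 through Sports.

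The sizes assume that 5 is a valid answer, as the stated ranges imply. The net effect on group means depends on how many boys enter or leave category 5, which the documents do not give. If decline predominates, an assumption that is plausible for mobility in DMD, the bias runs towards apparent benefit. PODCI is exploratory, so the primary MRS, PK and safety results are not affected. The correction should still be made before reporting.

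**What to change.** Confirm the response codes in the CRF and the questionnaire before editing anything. Then list in Appendix 3, by item number, every valid code and every code treated as missing, including any code other than 5 that means too young.

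- If 5 is a valid answer on Q10 to Q14, Q26, Q27, Q34 and Q35, remove the note from Happiness and exempt the four rescaled items on Transfer and Sports.
- If 5 does mean too young on any of them, keep the note there and correct the ranges and formulas. With 5 missing on all five items, Happiness would become raw 5 to 20, mean 1 to 4 and (4 - mean)/3 x 100. An item coded 1 to 4 needs no 3/4 rescaling.

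Check the programmed PODCI derivations against the corrected text before reporting.

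The cost is one look at the code list, a few words in Appendix 3 and a derivation check. Deleting the note without that look carries a risk of its own, because a true too-young answer would then be scored as the worst answer.

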Appendix 4 PUL Assessment

| 1.4 Performance of the Upper Limb Module for DMD 2.0 (PUL for DMD) Worksheet | | | | | | | | |
|---|--|------------------------------|--|--|--|--|---|---|
| Preferred arm (used for all tests):  Right  Left | | | | | | | | |
| Elbow extension ROM: Right: Left: e.g. full = 0° 10° contracture = -10° | | | | | | | | |
| Supination ROM: Right:  Full  ¾  ½  ¼ Left:  Full  ¾  ½  ¼ | | | | | | | | |
| Entry item A – start with A to identify starting point for subsequent tests. Circle score for each item. DO NOT INCLUDE IN TOTAL SCORE | | | | | | | | |
| Item | Description | 0 | 1 | 2 | 3 | 4 | 5 | 6 |
| A. | Entry item | No useful function of hands. | Can use hands to hold pen or pick up a coin or drive a powered chair | Can raise 1 or 2 hands to mouth but cannot raise a cup with a 200g weight in it to mouth | Can raise plastic cup with 200g weight in it to mouth using 1 or 2 hands | Can simultaneously raise both arms (to shoulder height with or without compensation) i.e. elbow bent or in extension | Can raise both arms simultaneously above head only by flexing the elbow (shortening circumference of the movement /using accessory muscles) | Can abduct both arms simultaneously elbows in extension in a full circle until they touch above the head. |
| For item A: A score of 3, 4, 5, 6 on item A, start with item 1 – on this page A score of, 1, 2 start with item 7 on page 2 | | | | | | | | |
| High level shoulder Dimension | | | | | | | | |
| Item | Description | 0 | 1 | 2 | Score | | | |
| 1 Score from Entry item above | Shoulder abduction both arms above head "Raise your arms out to the side and above your head – try and keep straight elbows" | Unable | Can raise both arms simultaneously above head only by flexing the elbow - with compensation | Can abduct both arms simultaneously elbows in extension in a full circle until they touch above the head | | | | |
| 2 | Raise both arms to shoulder height (elbows at shoulder height) "Raise your arms to shoulder level" | Unable | Can raise both arms to shoulder height either one at a time or with elbows flexed (with compensation) | Can raise both elbows to shoulder height without compensation e.g. simultaneously with elbows straight | | | | |
| 3 | Shoulder flexion to shoulder height (no weights) "Reach out and touch my hand" – | Unable | Able with compensation | Able without compensation | | | | |
| 4 | Shoulder flexion to shoulder height with 500g weight "Reach out and touch my hand" – | Unable | Able to lift 500g weight with compensation | Able to lift 500g weight without compensation | | | | |

High level shoulder Dimension (continued)

| Item | Description | 0 | 1 | 2 | Score |
|------|---|--------|---|--|-------|
| 5 | Shoulder flexion above shoulder height with 500 g weight Hand on lap – “give me the weight” | Unable | Able to lift 500g weight with compensation | Able to lift 500g weight without compensation | |
| 6 | Shoulder flexion above shoulder with 1 kg weight Hand on lap – “give me the weight” | Unable | Able to lift 1 kg weight with compensation | Able to lift 1 kg weight without compensation | |

Mid level elbow Dimension
Do these tests on all individuals

| Item | Description | 0 | 1 | 2 | Score |
|------|---|--------|--|--|-------|
| 7 | Hand(s) to mouth “Bring the cup to your mouth with one hand” | Unable | Able to bring 200g in cup with any compensation to mouth (can use more than one hand and / or bring head to hands) | Able to bring 200g in cup to mouth with one hand no elbow support (without compensation) | |
| 8 | Hands to table from lap “Bring both hands from lap to table” | Unable | Able to bring two hands completely (to wrist crease) to table but NOT simultaneously or in one action | Two hands completely on table simultaneously | |
| 9 | Move weight on table 100g “Move the weight from outside circle to centre circle” | Unable | Can move 100g weight from outer to centre circle using compensation (slide forearm or elbow make contact with table) | Can lift 100g weight from outer to centre circle without compensation | |
| 10 | Move weight on table 500g “Move the weight from outside circle to centre circle” | Unable | Can move 500g weight from outer to centre circle using compensation (slide forearm or elbow make contact with table) | Can lift 500g weight from outer to centre circle without compensation | |
| 11 | Move weight on table 1kg “Move the weight from outside circle to centre circle” | Unable | Can move 1kg weight from outer to centre circle using compensation (slide forearm or elbow make contact with table) | Can lift 1kg weight from outer to centre circle without compensation | |
| 12 | Lift heavy can diagonally “Lift can from this circle nearest your hand to this circle furthest away and across your body” | Unable | Can move heavy can from nearest circle across body with compensation (slide forearm or elbow make contact with table) | Can lift heavy can from nearest circle across body without compensation | |

Mid level elbow Dimension (continued)

| Item | Description | 0 | 1 | 2 | Score |
|------|---|--|---|--|-------|
| 13 | Stack of three cans "Stack these two cans, one at a time on the middle can using one hand" | Unable to stack third can even with compensation | Able to stack third can with compensation | Able to stack third can without compensation | |
| 14 | Stack of five cans "Stack these two additional cans, one at a time on top of this can using one hand" | Unable to stack fifth can even with compensation | Able to stack fifth can with compensation | Able to stack fifth can without compensation | |
| 15 | Remove lid from container "Use your hands to open this container" | Unable | Opens completely | | |

Distal wrist and hand Dimension
Do these tests on all individuals

| | | 0 | 1 | 2 | Score |
|----|--|--|--|--|-------|
| 16 | Tearing paper "Tear the sheet of paper beginning from here" | Unable | Tears the sheet of paper folded in half from the folded edge | Tears the sheet of paper folded in 4, beginning from the folded edge | |
| 17 | Tracing path "Use your pencil to complete the path in one smooth movement" | Unable | Completes the path with compensation - needs to raise pencil from paper or pivot arm | Able to complete the path without stops or raising hand from paper | |
| 18 | Push on light "Push on the light with the fingers of one hand" | Unable | Able to turn the light on momentarily with fingers of one hand | Able to turn the light on permanently with fingers of one hand | |
| 19 | Supination "Pick up the light and turn your hand over" | Unable | Picks up the light but either turns hands over incompletely or uses compensation to turn it over | Picks up the light, and turns the hand over completely with no compensatory movements | |
| 20 | Picking up coins "Using one hand, Pick up 6 coins, one at a time" | Cannot pick up one coin | Can pick up one coin/token | Can pick up six coins in one hand | |
| 21 | Placing finger on number diagram (precision not essential) "Using one finger to touch each number on the diagram" | Cannot raise the finger or slide it on the diagram | Able to place finger (slide or lift) between at least two squares | Able to place finger successively on the numbers of the diagram (with or without compensation) | |
| 22 | Pick up 10g weight finger pinch "Pick up this small weight like this (by body of weight)" | Unable | Able to grip and lift weight off surface | | |

